11.6 Sample Size Calculation

The present study was powered based on the results of a recent meta-analysis reporting a pooled TCD sensitivity of 96.1% for RLS detection, while the pooled TTE sensitivity was estimated at 45.1% (absolute difference of 51%)⁶. For power calculations, we used a more moderate effect size of 40% increase in the sensitivity of NB-IS TCD compared to TTE.

A sample size of 100 subjects achieves 90% power to detect a difference of 40% between two diagnostic tests whose sensitivities are 90% (TCD) and 50% (TTE). This procedure uses a two-sided McNemar test with a significance level of 0.05. The mean prevalence of PFO in the population of patients with cryptogenic stroke is at least 30%². The proportion of discordant pairs has been set at 0.500.

[figure not shown]
		Sensitivity	ity Sensitivity Proportion					
		of Test 1	of Test 2		Discordant	Prevalence		
Power	N	Se1	Se2	Se1-Se2	D	Р	Alpha	Beta
0.00000	10	0.900	0.500	0.400	0.500	0.300	0.05000	
	1.00000							
0.00830	20	0.900	0.500	0.400	0.500	0.300	0.05000	
	0.99170							
0.12990	30	0.900	0.500	0.400	0.500	0.300	0.05000	
	0.87010							
0.32013	40	0.900	0.500	0.400	0.500	0.300	0.05000	
	0.67987							
0.49003	50	0.900	0.500	0.400	0.500	0.300	0.05000	
	0.50997							
0.62345	60	0.900	0.500	0.400	0.500	0.300	0.05000	
	0.37655							
0.72404	70	0.900	0.500	0.400	0.500	0.300	0.05000	
	0.27596							
0.79937	80	0.900	0.500	0.400	0.500	0.300	0.05000	
	0.20063							
0.85654	90	0.900	0.500	0.400	0.500	0.300	0.05000	
	0.14346							
0.89995	100	0.900	0.500	0.400	0.500	0.300	0.05000	
	0.10005							
0.93182	110	0.900	0.500	0.400	0.500	0.300	0.05000	

DWF-C0001-001 CONFIDENTIAL Page 37 of 44

Protocol ID: NA-07BBL-01 Version Date: August 2, 2021

	0.06818						
0.95405	120	0.900	0.500	0.400	0.500	0.300	0.05000
	0.04595						
0.96898	130	0.900	0.500	0.400	0.500	0.300	0.05000
	0.03102						
0.97890	140	0.900	0.500	0.400	0.500	0.300	0.05000
	0.02110						
0.98561	150	0.900	0.500	0.400	0.500	0.300	0.05000
	0.01439						

 $\label{eq:vsN} vs~N$ Se1=0.900 Se2=0.500 D=0.500 α =0.050 P=0.300 2-Sided McNemars Test

Given previous reports indicating a prevalence of suboptimal transtemporal windows in 5% of Hispanic²⁰, 5% of Caucasian²¹, 9% in African American¹⁹ and 14% of Asian²² individuals aged <60 years, we increased our projected sample size by 20% (n=120). In addition, the final sample size

DWF-C0001-001 CONFIDENTIAL Page 38 of 44

was further increased by 20% (n=144) in order to account for an anticipated dropout rate of 20%. Consequently, the final study sample was set at 144 individuals.

The sensitivity of TCD against TEE for right-to-left shunt detection has been estimated 90% in a recent meta-analysis²⁴. A sample size of 147 patients produces a two-sided 95%CI with a 95%CI width equal to 20% when the sample sensitivity is 90% and the prevalence is 30%. After the first 150 TTE subjects in the Main study are enrolled, the study will continue to enroll up to an additional 150 subjects that received a TTE or TEE bubble study.

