11 STATISTICAL ANALYSIS

11.1 Primary Endpoint Analysis

- Demonstration of NB-IS TCD diagnostic performance for shunt detection, as compared to transthoracic echocardiography (TTE) for diagnostic accuracy.
 - Diagnostic Accuracy Shunt detection rate (%)

> % detection of true positives (TP) (sensitivity), all sample size estimations will be computed with regard to the endpoint of sensitivity

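### Section 11.6 should name its McNemar test: the table was computed with the conservative exact conditional version, and the unconditional exact version gives about 92% rather than 89% average power at N = 100

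*Combined protocol and SAP*

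**What the plan says.** Section 11.6 states that "A sample size of 100 subjects achieves 90% power to detect a difference of 40% between two diagnostic tests", with sensitivities of 90% for TCD and 50% for TTE. It adds: "This procedure uses a two-sided McNemar test with a significance level of 0.05". It sets prevalence at 0.30 and says of discordance: "The proportion of discordant pairs has been set at 0.500". The table beneath runs from N = 10 to N = 150 and reads 0.89995 at N = 100.

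Section 11.1 takes sensitivity as the primary measure and says that "all sample size estimations will be computed with regard to the endpoint of sensitivity", but it names no test. Section 11.5 sets the success criteria, one of which is a 40% increase in sensitivity over TTE; it names no test either. Nowhere does the plan say whether the McNemar test is exact conditional, unconditional exact, mid-p or asymptotic.

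**The concern.** McNemar's test exists in several versions, and with few discordant pairs they can disagree on the same data. The plan expects about 30 × 0.500 = 15 discordant pairs. Suppose 16 occur and split 12 to 4. The exact conditional p-value is 0.077, the asymptotic 0.046 and the mid-p 0.049. While the version is unnamed, significance could depend on a choice made after the data are seen.

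The version behind the power table is also the conservative one. At this size its true type I error is well below 5%, and power is lost with it. A test that still guarantees 5% can recover some of that power from the same subjects.

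**Working it through.** **Inputs (section 11.6).** Sensitivities 0.90 and 0.50, discordance D = 0.500, prevalence 0.30, two-sided α = 0.05.

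- Positives at N = 100: n = 100 × 0.30 = 30.
- Let p10 be the probability that TCD is positive and TTE negative among shunt-positives, and p01 the reverse. Then p10 + p01 = 0.50 and p10 − p01 = 0.40, so p10 = 0.45 and p01 = 0.05.

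**Method.** Let b and c be the two discordant counts among n positives. Then (b, c, n − b − c) is multinomial with probabilities (p10, p01, 1 − p10 − p01). Power is the sum of these probabilities over the rejection region. Size is the same sum with p10 = p01 = D/2. The exact conditional test rejects when 2·P(X ≤ min(b, c)) ≤ 0.05, with X ~ Binomial(b + c, 0.5).

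**Step 1: reproduce the table.** At N = 20 there are 6 positives. Six discordant pairs in one direction give p = 2 × 0.5^6 = 0.031; five give 2 × 0.5^5 = 0.0625. Rejection therefore needs all six one way, and power is 0.45^6 + 0.05^6 = 0.00830, as tabulated. Other rows:

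| N | n | Plan | Exact conditional | Mid-p | Asymptotic | Continuity-corrected |
|---|---|---|---|---|---|---|
| 20 | 6 | 0.00830 | 0.00830 | 0.06366 | 0.21746 | 0.00830 |
| 50 | 15 | 0.49003 | 0.49003 | 0.62822 | 0.65555 | 0.49003 |
| 100 | 30 | 0.89995 | 0.89995 | 0.93682 | 0.93698 | 0.89320 |
| 150 | 45 | 0.98561 | 0.98561 | 0.99141 | 0.99277 | 0.98371 |

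Only the exact conditional test matches all 15 rows.

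**Step 2: true size of that test at n = 30.** It is 2.4% at D = 0.40, 2.8% at D = 0.50, 3.0% at D = 0.60, and at most 4.3% (at D = 1).

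**Step 3: the unconditional exact test.** Order outcomes by |b − c|/√(b + c) and take the largest rejection region whose size, maximised over D, stays at or below 0.05. At n = 30 the cutoff is 2.00, the maximum size is 4.9%, and power is 0.937. The 12 to 4 split above gives 8/√16 = 2.00 and is rejected.

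**Step 4: the gain depends on the realised number of positives.**

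| n | Exact conditional | Unconditional exact | Gain (points) |
|---|---|---|---|
| 27 | 0.857 | 0.880 | 2.4 |
| 30 | 0.900 | 0.937 | 3.7 |
| 32 | 0.922 | 0.935 | 1.3 |
| 45 | 0.986 | 0.991 | 0.6 |

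(Gains are taken before rounding.) Thirty is only the expected number. Weighting each n by Binomial(100, 0.3) gives 0.886 for the exact conditional test and 0.920 for the unconditional exact test, a gain of 3.4 points.

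**Step 5: mid-p.** Its average power is 0.926, but its maximum size exceeds 5% at some n: 6.4% at n = 24 and 6.1% at n = 29, both at D = 1. For D up to 0.7 it stays at or below about 4.9% for every n from 24 to 44.

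**Step 6: is about 30 positives realistic?** The planned 144, less the plan's 20% dropout and 5% to 14% poor windows, leaves 144 × 0.80 × 0.86 = 99 to 144 × 0.80 × 0.95 = 109 evaluable subjects. At 30% prevalence that is 30 to 33 positives.

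**The case against.** **The plan contains no error.** The exact conditional test is valid and widely used, and 90% is its correct power at 30 positives. Planning on the expected number of positives is ordinary practice, and 88.6% is only 1.4 points below the claim. All of this stands.

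**A reader might infer that the trial gives away almost half its alpha.** The documents do not support that. The conditional version is identified from the power table, whereas section 11.1 leaves the analysis test open. An asymptotic analysis would have power of about 0.937 at 30 positives, although its maximum size there is 5.4%. The 2.8% is also specific to n = 30 and D = 0.50.

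**A reader might infer that any less conservative version comes free.** That is not so for mid-p, as step 5 shows, although the excess arises only at discordance far above the plan's 0.50.

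**The choice may not affect success at all.** If the 40% increase in section 11.5 means an observed difference of at least 40 points, success at n = 30 requires b − c ≥ 0.40 × 30 = 12. The least significant such outcome is b = 21, c = 9, with exact conditional p = 0.043. Every success at n = 30 is then already significant, and changing the test alters no decision there. This limits the point to the reading in which success means p < 0.05.

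**The gain shrinks under better conditions.** Section 11.6 says "The mean prevalence of PFO in the population of patients with cryptogenic stroke is at least 30" per cent, and the 40-point difference was chosen as more moderate than the 51 points in its source. At 51 points and 30 positives, conditional power is already 0.982 to 0.999 for D from 0.51 to 0.60. This also stands.

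**Conclusion.** This is a worthwhile low-cost improvement and a gap in pre-specification, not a mistake in the power calculation. The version of the McNemar test is unnamed, and the tabulated one is conservative at the planned size. At N = 100 under the plan's assumptions (sensitivities 0.90 and 0.50, D = 0.50, prevalence 0.30), the unconditional exact test raises average power from 88.6% to 92.0% while holding size at or below 5%. The gain varies with the number of positives and is about 0.6 points at 45. It rests on about 100 subjects being evaluable and on success being judged by p < 0.05.

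**What to change.** In sections 11.1 and 11.6, name the unconditional exact (Suissa-Shuster) McNemar test, two-sided 0.05, as the primary test of NB-IS TCD against TTE. Keep the sample size. Restate power at N = 100 as about 92% averaged over the random number of positives (93.7% if exactly 30).

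If the sponsor keeps the exact conditional test, name it and state about 89% average power. If mid-p is preferred for its simplicity, state that its size can exceed 5% at some n under extreme discordance.

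The cost is one sentence, one restated figure and a named software routine for the unconditional test. Trial conduct does not change.

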5 STUDY DESIGN

This study is a multi-center, prospective, single-arm, non-significant risk (NSR) device study in which up to 150 evaluable subjects with embolic stroke of undetermined source (ESUS) according to standardized criteria¹³ will be evaluated with NB-IS TCD and standard of care TTE to screen for right to left shunt (RLS) or patent foramen ovale (PFO). Additionally, up to 150 evaluable subjects will be evaluated with NB-IS TCD and standard of care TTE or TEE.

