5.1 Study Population Size

To ensure the study is adequately powered, up to 150 subjects will be enrolled at up to 7 centers in the US. The estimation of this sample size has taken into account the prevalence of suboptimal transtemporal windows and potential dropouts.

Once the 150 TTE subjects are enrolled, the study will continue to enroll up to another 150 subjects that received a TTE or TEE until enough TTE subjects have been enrolled in the different grades of the International Consensus Criteria (0,1,2,3) across the TTE Main Study and TTE/TEE Sub Study combined.

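### Section 11.6 sets the final sample at 144 to cover 20% dropout from 120, but 144 leaves 115; 150 is needed (minor text correction, little effect on power)

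*Combined protocol and SAP*

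**What the plan says.** Section 11.6 builds the Main Study size in three steps.

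- It takes 100 subjects for 90% power, using a two-sided McNemar test at 0.05 with sensitivities of 90% (TCD) and 50% (TTE), discordant proportion 0.500 and prevalence 30%.
- It cites suboptimal windows in 5% to 14% of individuals under 60, depending on ethnic group, and states "we increased our projected sample size by 20% (n=120").
- The result "was further increased by 20% (n=144) in order to account for an anticipated dropout rate of 20" per cent. "Consequently, the final study sample was set at 144 individuals".

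Elsewhere the working number is 150, and it is described in two ways. Section 5, like the synopsis, speaks of "up to 150 evaluable subjects with embolic stroke of undetermined source (ESUS"). Section 5.1 says "up to 150 subjects will be enrolled at up to 7 centers in the US" and adds: "The estimation of this sample size has taken into account the prevalence of suboptimal transtemporal windows and potential dropouts". Section 6.1 counts a subject as enrolled once consent is signed. Section 6.3 removes subjects with inadequate scans from the final analysis, so enrolled and evaluable are different counts.

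Section 11.6 then gives a precision figure for sensitivity against TEE: "A sample size of 147 patients produces a two-sided 95%CI with a 95%CI width equal to 20% when the sample sensitivity is 90" per cent and prevalence is 30%. It goes on to describe enrolment of "up to an additional 150 subjects that received a TTE or TEE bubble study".

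**The concern.** The dropout step confuses inflation with loss. To have n subjects left after a fraction d is lost, one enrols n/(1 − d), not n(1 + d). The figure of 144 therefore does not do what its own sentence says it does, and it is declared to be the final study sample.

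Two things are at stake: whether the primary comparison keeps its planned 90% power after losses, and whether a reader can tell if the stated sample is counted before or after those losses. The ceiling of 150 happens to equal the correct figure. However, Section 11.6 does not derive it, and the synopsis and Section 5 attach the word evaluable to it while Section 5.1 treats it as the number enrolled.

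**Working it through.** **Inputs, all from Section 11.6:** base N = 100; sensitivities 0.90 and 0.50; discordant proportion 0.50, which gives discordant cells of 0.45 and 0.05; prevalence 0.30; two-sided alpha 0.05; dropout 20%; cited window losses 5–14%.

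**1. Reproduce the plan's power table.** I used exact two-sided McNemar (binomial) power on 0.3 × N shunt-positive subjects.

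| N | Positives | Recomputed power | Plan's table |
|---|---|---|---|
| 90 | 27 | 0.85654 | 0.85654 |
| 100 | 30 | 0.89995 | 0.89995 |
| 110 | 33 | 0.93182 | 0.93182 |
| 120 | 36 | 0.95405 | 0.95405 |
| 150 | 45 | 0.98561 | 0.98561 |

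The base of 100 is confirmed.

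**2. Reproduce the inflation.** 100 × 1.2 = 120, and 120 × 1.2 = 144. These are the plan's figures.

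**3. Check the dropout step.**

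- Left after 20% dropout from 144: 144 × 0.8 = 115.2, about 5 short of 120.
- Needed to keep 120: 120/(1 − 0.20) = 150.
- Largest dropout at which 144 still keeps 120: 1 − 120/144 = 16.7%.

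**4. Effect on primary power, Main Study alone.** Evaluable number = enrolled × 0.8 × (1 − window loss). Power is interpolated between whole numbers of positives. The last row uses up the plan's own window allowance: going from 100 to 120 allows for 20 lost out of 120, or 16.7%.

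| Window loss | 144 enrolled: evaluable | Power | 150 enrolled: evaluable | Power |
|---|---|---|---|---|
| 5% | 109.4 | 0.930 | 114.0 | 0.942 |
| 14% | 99.1 | 0.896 | 103.2 | 0.911 |
| 16.7% | 96.0 | 0.884 | 100.0 | 0.900 |

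**5. The TEE precision figure.** 147 × 0.30 = 44.1 positives. At 90% sensitivity the exact (Clopper-Pearson) 95% interval has width 0.198, so the stated 20% reproduces.

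**The case against.** The strongest reply is that nothing of substance depends on 144. The power target is 100 evaluable subjects, and 120 is only an intermediate step. The window step exceeds every cited window rate, so its slack absorbs most of the dropout slip. Keeping 100 evaluable needs 100/(0.8 × 0.95) = 132 enrolled at 5% window loss and 100/(0.8 × 0.86) = 145 at 14%, so 144 is at worst about one subject short at the cited rates. Section 6.3 requires only a unilateral signal, so the cited rates may overstate the loss. The operating ceiling is already 150. All of this stands, and it limits the point to a text correction. It does not make 144 the right answer to the sentence that produces it.

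A reader might be tempted by four stronger conclusions that the documents do not support.

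- *The primary comparison is underpowered.* At the cited window losses, power stays at about 0.90 or above even with 144 enrolled.
- *The window step is wrong in the same way, so even 150 falls below 90% power.* This would need a 20% window loss, which no section states. The cited range is 5–14%, and using the full allowance is a 16.7% loss.
- *Enrolled and evaluable contradict each other.* Both figures are ceilings (up to 150). Section 5.1 says its number already allows for windows and dropouts, which points to enrolled. The wording is inconsistent, but the intended meaning can be inferred.
- *The TEE precision figure is wrong or the TEE sample is short.* The figure of 147 is correct. Section 11.6 never says that the added cohort will supply 147 TEE pairs, and Section 5 also describes that cohort as evaluable. TEEs done in the Main Study under standard of care may add pairs. TEE is in neither success criterion in Section 11.5. The absence of a projected TEE count is missing detail, not an error.

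**Conclusion.** The stated final sample of 144 is wrong for its stated purpose; the correct figure is 150. The shortfall is 6 enrolled subjects, or about 5 retained.

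The consequence for the primary analysis is small: correcting 144 to 150 moves expected power from 0.90–0.93 to 0.91–0.94 at the cited window losses. With the whole window allowance used, 150 enrolled returns exactly the 100 subjects on which the 90% power rests, whereas 144 gives 0.884.

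These figures assume the plan's sensitivities, discordance and prevalence, 20% dropout, window losses that apply on top of dropout, and the Main Study alone. The cited window rates are for people under 60, while the trial admits adults of any age. TTE subjects in the added cohort would raise the figures if they enter the primary analysis, which the plan does not state.

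**What to change.** - In Section 11.6, replace 144 with 150, shown as 120/0.8, and call it the final enrolled sample.
- Use *enrolled* for the Main Study 150 in the synopsis, Section 5 and Section 5.1.
- State the expected evaluable number and power: about 103–114 and 0.91–0.94 at 20% dropout and the cited window losses, with a floor of 100 and 0.90 if the full window allowance is used.
- Optionally, note that the 20% width applies to 147 evaluable NB-IS/TEE pairs, a count the plan does not project.

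The cost is a text change only. No subjects, procedures or enrolment rules are added, because the ceiling is already 150.

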11.7 Primary Safety Endpoint Analysis

Throughout the study we will collect the incidence of device-related adverse events, which will be used to determine the safety of the device within the acute stroke environment. In our EXPEDITE study which is also run in the ER for stroke assessment, the device has been designated minimal risk by the IRB and we have not had any serious adverse events in over 80 subjects. We will continue to closely monitor this metric.

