4.1 Primary Efficacy Endpoint

 % detection of RLS/PFO with NB-IS TCD compared against standard of care Transthoracic Echocardiography (TTE)

4.2 Secondary Technical Efficacy Endpoints:

- % agreement for detection of RLS/PFO with NB-IS TCD vs SOC TCD
- % agreement for detection of RLS/PFO with NB-IS TCD vs Transesophageal Echocardiography (TEE)
- % agreement for detection of clinically significant shunts with NB-IS TCD vs TTE
- No window rate (including both unilateral and bilateral absent acoustic windows)
- Success rate of the NB-IS TCD
- Incidence of NB-IS device malfunctions

4.3 Exploratory Endpoints:

 Development of an automated algorithm for Spencer Logarithmic Scale¹⁰ and International Consensus Criteria grading of RLS¹¹

4.4 Primary Safety Endpoint:

Incidence of device-related serious adverse events.

4.5 Secondary Safety Endpoints:

Incidence of procedure-related adverse events related to agitated saline injection before and after VM (headache, allergic reactions, new onset neurological deficit, ischemic stroke, TIA or

DWF-C0001-001 CONFIDENTIAL Page 18 of 44

pulmonary embolism complicating agitated saline contrast injection, etc) will be closely monitored and prospectively collected¹².

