7.1 Known Potential Risks

The following device-related adverse events have been identified as possible (anticipated) with the use of the NeuralBot Investigational System:

- Physical discomfort of the head and neck due to pressure from the probe, or probe accidentally coming in contact with ears, eyes or hair.
- Psychological feeling of claustrophobia- the fear of being enclosed in a small space.

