8.2 Reporting Device and/or Procedure Related Adverse Events

All suspected device related adverse events shall be recorded on the Adverse Event page of the CRF if they are suspected to be related to the use of the NeuralBot Investigational System. If appropriate, the event shall subsequently be reported to the relevant IRB. The event shall be thoroughly investigated and a causal relation as to whether the event is related or not to the use of the NeuralBot Investigational System shall be established.

The Investigator will record the nature, severity, relatedness, treatment, and outcome of the AE. This classification of the event determines the reporting procedures to be followed. NovaSignal may upgrade the classification as required for reporting purposes.

At the initiation of device use through end of use of the device, all subjects with adequate quality NeuralBot Investigational System data shall be assessed for any potentially device related complications or adverse events. All events shall be followed until resolution or through the end of a subject's study participation.

Device-related adverse events information will be collected throughout the study. From the initiation of and end of device use, all subjects scanned with the NeuralBot Investigational System shall be assessed for any potentially device related complications or adverse events. All events shall be followed until resolution or through the end of a subject's study participation.

Procedure-related adverse events related to agitated saline injection before and after VM (headache, allergic reactions, new onset neurological deficit, ischemic stroke, TIA or pulmonary embolism complicating agitated saline contrast injection, etc) will be closely monitored and prospectively collected¹⁸. Nevertheless, it should be noted that a recent multi-center study underlined the safety and importance in performing TCD-BS for RLS detection in a standardized manner using the currently recommended international consensus protocol with agitated saline intravenous injections¹⁹.

Event, onset date, severity, relatedness, device relationship, treatment and outcome of the AE will be recorded on the appropriate case report form. Any device-related and/or procedure-related AEs will be monitored until they are adequately resolved or explained. This classification of the event determines the reporting procedures to be followed. For purposes of this protocol, the following definitions will apply.

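### The primary safety endpoint counts serious device-related events in 4.4 but all device-related events in 11.7, and 8.2 and 6.3 leave the safety population unsettled

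*Combined protocol and SAP*

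**What the plan says.** **Endpoint.** Section 4.4 gives the primary safety endpoint as "Incidence of device-related serious adverse events", and the synopsis agrees. Section 11.7, the analysis of that endpoint, states that "we will collect the incidence of device-related adverse events, which will be used to determine the safety of the device". It then reports, for another study with the device, that "we have not had any serious adverse events in over 80 subjects", and closes with "We will continue to closely monitor this metric". It names no denominator, estimator, interval or criterion.

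**Who is assessed.** One paragraph of 8.2 says that "all subjects with adequate quality NeuralBot Investigational System data shall be assessed for any potentially device related complications or adverse events". The next says that "all subjects scanned with the NeuralBot Investigational System shall be assessed for any potentially device related complications".

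**Who is analysed.** Section 6.3 calls a study adequate when a signal on at least one side, at the stated depth, is recorded throughout the bubble study at rest and with Valsalva. If a scan falls short, 6.3 takes all of that subject's clinical and imaging data out of the final analysis. Safety data are not excepted.

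**Expected events.** Section 7.1 anticipates claustrophobia and "Physical discomfort of the head and neck due to pressure from the probe".

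**The concern.** The section that should carry out the primary safety analysis describes a broader endpoint than the one defined. The events expected in 7.1 would ordinarily be non-serious under 8.1.2, so they would count under 11.7 and usually not under 4.4.

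The denominator is also open, and 6.3 ties exclusion to whether the session was completed. A session can be cut short for a reason connected with the device: 6.7 and 6.8 end a scan when the ALARA limits are reached, and section 7 allows use of the device to be discontinued at any time for any reason. An event in such a session is one that a safety analysis should keep.

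The study is labelled pivotal, and section 7 says the device's risks in humans are not yet established. With the definition unsettled, it could be chosen after the results are known.

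**Working it through.** The plan gives no safety figure to reproduce: 11.7 has no sample size, threshold, significance level or interval. The check is a comparison of texts, followed by arithmetic on what the choices can change.

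**1. Numerator**

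| Place | What is counted |
|---|---|
| Synopsis; 4.4 | Device-related serious adverse events |
| 11.7, operative sentence | Device-related adverse events, seriousness not mentioned |
| 11.7, supporting sentence | Serious adverse events in another study |
| 11.7, last sentence | An unnamed metric, which could be either |

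**2. Population**

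| Place | Subjects |
|---|---|
| 8.2, one paragraph | Those with adequate-quality data |
| 8.2, next paragraph | All scanned |
| 6.3 | Inadequate scans leave the final analysis, clinical data included |
| 11.7 | Not stated |

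Two numerators and two populations give four possible results.

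**3. Precision if no event is seen.** The exact two-sided 95% upper limit for 0 of n is U = 1 − 0.025^(1/n).

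- n = 150 (main study maximum, 5.1): U = 2.4%.
- n = 300 (150 + 150, 5.1 and 11.6): U = 1.2%.
- n = 80 (the floor of the prior experience in 11.7): U = 4.5%.

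**4. Effect of the population on that limit.** The documents give no rate of inadequate scans. I assume 5%, 14% and 20%. The first two are the ends of the range of suboptimal windows cited in 11.6, and the third is the plan's own allowance. None is a measured rate of inadequate scans, because the cited figures are for people under 60 and 6.3 needs a signal on one side only.

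| Scanned | Left after 5% / 14% / 20% | U for zero events |
|---|---|---|
| 150 | 142 / 129 / 120 | 2.6% / 2.8% / 3.0% |
| 300 | 285 / 258 / 240 | 1.3% / 1.4% / 1.5% |

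**5. One serious event in an inadequate scan (assumed).** Among all 300 scanned the result is 1/300 = 0.33% (exact 95% CI 0.01% to 1.84%). With 14% excluded it is 0/258 = 0% (0% to 1.42%). The one event disappears.

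**6. Effect of the numerator.** In a fixed population, the two readings differ by the proportion of subjects whose device-related events were all non-serious. The documents do not give it. If 1% to 10% of 300 subjects (3 to 30) had any device-related event, 11.7 read literally would report 1% to 10%. At 15/300 the figure is 5.0% (95% CI 2.8% to 8.1%). The 4.4 rate could still be zero.

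**7. Direction of any bias.** Let f be the fraction of inadequate scans, and R_A and R_I the event rates in adequate and inadequate scans. The rate in all scanned subjects is (1 − f)·R_A + f·R_I. Reporting R_A alone misses it by f·(R_I − R_A). None of the three quantities is in the documents. Sessions stopped for discomfort would raise R_I. Subjects with no window could lower it: under 6.7 they have the search of up to 20 minutes but not the monitoring of up to 20 minutes that follows. The sign is undetermined.

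**The case against.** The strongest reply is that this is loose drafting. The endpoint is defined twice in the same terms, 11.7 bears its name, and the sentence about the other study speaks of serious events, so the closing reference to a metric may well mean those. Serious events are a subset of the events collected, so either count can be produced from the same case report forms. That makes the intention plausible, but the sentence that says what will determine safety is still unrestricted.

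On population, a reader might infer from the adequate-quality sentence that subjects whose session failed are never assessed for harm, and that the safety rate is therefore biased downward. The documents do not support this. The two sentences in 8.2 are nested, so assessing everyone scanned satisfies both. Section 8.2 also requires every suspected device-related event to be recorded without a quality condition, 8.1.1 starts collection after consent, and the schedule marks these events as required. The data will be collected. It is 6.3 that can take them out of the analysis, and the direction of the effect is unknown (step 7).

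Nor is every stopped scan inadequate. Section 6.12.4 completes the supine rest and Valsalva recordings before repeating them at 45 degrees, and the 6.3 definition does not mention head position. A stop after the supine pair may still count as adequate.

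Two further inferences also fail. Agitated-saline events are a secondary safety endpoint (4.5, 11.8), so they are not lost because 8.3.2 attributes events to device or procedure. And 11.7 states no rule that zero events means the device is safe; it simply gives no interval.

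**Conclusion.** The point holds as two inconsistencies in the current text. Section 11.7 does not analyse the endpoint that 4.4 and the synopsis define. The safety population is stated two ways in 8.2, is not named in 11.7, and is exposed to an exclusion in 6.3 that makes no exception for safety.

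The consequence is ambiguity in the primary safety result. Safety has no hypothesis, threshold or significance level, and the success criteria in 11.5 concern efficacy only, so no error rate, power or sample size changes. If no serious device-related event occurs, the choice of population moves only the upper limit: at 300 scanned, from 1.2% to between 1.3% and 1.5% under the assumed exclusion rates. If one occurs in an inadequate scan, the choice decides whether it appears in the analysis. The choice of numerator can matter more, by an amount the documents do not fix.

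Confidence is high on the wording conflicts. No claim is made about the size or direction of bias. The change should be made before results are known.

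**What to change.** 1. **Section 11.7.** Analyse the 4.4 endpoint: number and percent of subjects with at least one device-related serious adverse event, with an exact 95% confidence interval. Put all device-related adverse events in a separate supportive table. State whether the main study and the TTE/TEE sub-study are pooled, since this decides which zero-event limit applies.
2. **Section 8.2.** Delete the adequate-quality sentence. Use one safety population, every subject in whom NB-IS set-up was started, whatever the scan quality, and word the remaining sentence to match. This is slightly wider than all subjects scanned, because it keeps the failed registrations listed in 11.2.
3. **Section 6.3.** Limit the exclusion of inadequate scans to the efficacy analyses, so that safety data stay in. Without this step, the edit to 8.2 leaves the conflict in place.

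The cost is wording in three sections and one extra table, with no new data. The downside is that the reported safety rate may look slightly less favourable.
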